#### 1.4.1 Rationale for Dose Selection

**PVSRIPO:** As noted, the dose for PVSRIPO treatment and retreatment (if applicable) was selected based on IND-directed toxicity studies and the Phase 1 study (Pro00031169;

ClinicalTrials.gov Identifier: NCT01491893) in adults with rGBM (n=61) and is supported by the data in over 100 patients in the ongoing multicenter Phase 2 study (Pro00077024; ClinicalTrials.gov Identifier: NCT02986178). The PVSRIPO dose identified in the Phase 1 study, being used in the Phase 2 study and to be utilized in this study is  $5 \times 10^7$  TCID50.

**Pembrolizumab:** The recommended dose of pembrolizumab is keeping with prior investigations in rGBM [3, 4, 20, 21] that were well tolerated: 200 mg administered as an IV infusion over 30 minutes every 3 weeks. Treatment is planned to continue up to a maximum of Week 104 (approximately 23.5 months), until confirmed disease progression or unacceptable toxicity leading to discontinuation.

## 2 Study Objectives and Endpoints

### 2.1 Efficacy, Safety, and Exploratory Objectives and Endpoints

The study objectives and corresponding endpoints are described in greater detail below and are summarized in **Table 2**. Endpoints evaluated by iRANO criteria will focus on patients treated with PVSRIPO followed by at least one dose of pembrolizumab.

#### 2.1.1 Primary Efficacy Endpoints

- ORR: Proportion of patients with confirmed CR or PR.
- DOR: KM curves showing median DOR for all patients that have confirmed CR or PR.
- DRR: Proportion of patients with confirmed response (CR or PR) that lasts for  $\geq 6$  months.

Objective response (CR or PR), stable disease and confirmed progression will be determined via criteria noted in **Table 3**.

#### 2.1.2 Primary and Secondary Safety Endpoints

**Primary:** Safety and tolerability, including assessment of DLT, will be assessed by evaluating the frequency and severity of TEAE via CTCAE (v5.0) when PVSRIPO is followed by at least one dose of pembrolizumab.

**Secondary:** Patients receiving PVSRIPO alone will also be summarized for frequency and severity of TEAE but separately and as a secondary endpoint.

**Table 2 Summary of Study Objectives and Endpoints**

Objectives	Endpoints/Evaluation Criteria
Primary (efficacy)	
Anti-tumor activity:	
 
• ORR: Proportion of patients with confirmed CR or PR.
 
• DOR: KM curves showing median DOR for all patients that have confirmed CR or PR.
 
• DRR: Proportion of patients with confirmed response (CR or PR) that lasts for <math>\geq</math> 6 months. Radiographic outcomes will be assessed via iRANO criteria [1] in this protocol.
 

Primary (safety)	
Safety/tolerability:	
 
• Frequency and severity of TEAE via CTCAE (v5.0) for patients receiving PVSRIPO and at least one dose of pembrolizumab.
 

Secondary (efficacy)	
Anti-tumor activity:	
 
• DCR: Comprised of patients achieving CR, PR or SD for <math>\geq</math> 6 months.
 
• DDC: KM curves showing median DDC for patients with confirmed CR, confirmed PR or SD for <math>\geq</math> 6 months.
 

Survival	
 
• Overall and landmark survival: Proportion of patients alive at <math>\geq</math> 6, <math>\geq</math> 12 and at 24 months post-PVSRIPO infusion as calculated by Kaplan-Meier methods.
 

Progression free survival	
 
• If calculable, PFS will be estimated based on the time from PVSRIPO infusion to death or confirmed progression, based on the definition of progression noted in Table 3.
 

Secondary (safety)	
	
 
• Frequency and severity TEAE via CTCAE for patients receiving PVSRIPO alone without pembrolizumab (any reason).
 

Exploratory	
Identification of biomarkers of anti-tumor response to PVSRIPO followed by pembrolizumab	Assessment of tumor tissue and blood samples for identification of genetic, cytologic, histologic and/or other markers that demonstrate pharmacodynamic activity of PVSRIPO or correlate with anti-tumor response.
Alternative assessment of radiographic response/progression/PFS	
Radiographic outcomes will also be analyzed as described in Table 3 for endpoint determination.
 
All response must be confirmed via two consecutive MRI assessments at least 4 weeks apart. If on bevacizumab therapy when response first noted, response will be confirmed <math>\geq</math> 8 weeks off bevacizumab, via MRI.

Patient-reported outcomes	Assessment of patient-reported quality of life and activities of daily living capabilities

## 2.2 Secondary Efficacy Endpoints

Secondary efficacy endpoints will include the following and will be assessed through a maximum of 24 months post-PVSRIPO infusion:

- DCR: Comprised of patients achieving CR, PR or SD for  $\geq$  6 months.
- DDC: KM curves showing median DDC for patients with confirmed CR, confirmed PR or SD for  $\geq$  6 months.
- Overall and landmark survival: Proportion of patients alive at  $\geq$  6,  $\geq$  12 and 24 months post-PVSRIPO infusion as calculated by Kaplan-Meier methods.
- Progression free survival: Calculated from the time of PVSRIPO infusion to death or confirmed progression via the definition outlined in **Table 3**.

## 2.3 Exploratory Endpoints

Exploratory endpoints include assessment of changes in markers of immune function from baseline and identification of genetic, cytologic, histologic and/or other markers (ie, biomarkers) that may correlate with response via analysis of biologic samples (includes blood, serum, cells, tumor biopsy).

In addition, radiographic response and PFS as determined via iRANO criteria will also be explored, and patient-reported outcomes will be assessed over the course of treatment.

## 3 Study Design

To establish therapeutic intent and adequately assess the risk/benefit profile, in the first protocol amendment, the study sample size was adjusted to allow for sufficient statistical power to demonstrate a meaningful difference in response, relative to monotherapy, and efficacy was elevated to a primary endpoint.

This is an open-label, single-arm, non-randomized study characterizing the efficacy, safety and tolerability of PVSRIPO delivered via intratumoral infusion followed by pembrolizumab in patients with rGBM.

Approximately 30 eligible participants, 18 years of age or older, will be enrolled and treated with PVSRIPO and at least a single dose of pembrolizumab in this study. The maximum planned duration of follow-up in this study is up to 24 months (104 weeks), and consists of the following treatments:

- Single PVSRIPO infusion at baseline.
  - Note: retreatment with PVSRIPO is allowed for qualifying patients with enhancing disease  $\geq$  12 months from initial PVSRIPO infusion
- Pembrolizumab (200 mg IV infusion) initiated 14 days after PVSRIPO infusion (up to 28 days, if necessary), given q 3 weeks, through Week 104 (23.5 months of treatment) or until irAE meeting criteria for dose interruption/discontinuation or confirmed progression (must consider clinical and radiographic assessments as outlined in **Section 8.4.6.1** and **Table 3**)

Patients reaching 24 months on this study may be offered participation in a longer-term follow-up/PVSRIPO retreatment protocol or other mechanisms.

The study will occur in the following periods as outlined in **Table 1** and **Figure 1**.

- Screening Period 1: Between 1 and 6 weeks prior to catheter placement
- Screening Period 2: Within 7 days of catheter placement
- PVSRIPO Catheter Placement and Biopsy (if required) Period: Day 0
- PVSRIPO Infusion Period/Baseline: Single PVSRIPO infusion at Day 0 or Day 1 (unless extension granted by Sponsor)
- Post-PVSRIPO infusion, pembrolizumab treatment and follow-up Period: pembrolizumab starting at Week 2 (up to Week 4, max) and every 3 weeks thereafter, to a maximum of Week 104 (approximately 23.5 months maximum pembrolizumab treatment duration)

Participants with enhancing disease  $\geq$  12 months from a prior PVSRIPO infusion and meet the key IC/EC for retreatment will be eligible for additional PVSRIPO infusion(s).

The study may be adapted or expanded in one or more larger cohorts of participants, in consultation with the DSMB, based on interim review and considering the totality of the study data.

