## NOTICE REGARDING IMMUNOPROGRESSION

**DUE TO KNOWN PVSRIPO-MEDIATED TREATMENT EFFECTS, INCREASED TUMOR SIZE ON RADIOGRAPHIC IMAGING FOLLOWING PVSRIPO ADMINISTRATION MAY OCCUR. EXCEPT IN CASES OF IMMINENT LIFE-THREATENING EMERGENCY, CONSULT WITH SPONSOR OR THEIR DESIGNEE PRIOR TO INITIATING NON-PROTOCOL-SPECIFIED TUMOR TREATMENTS OR PERFORMING SURGICAL RESECTION.**

- PVSRIPO's immune-mediated mechanism of action (MOA) is known to result in atypical tumor imaging responses that can manifest as polycystic or pseudopressive appearance, including areas of new enhancement and tumor enlargement (termed immunoprogession) that can persist for up to 6 or more months after infusion. Thus, reliance on radiographic imaging standard criteria (eg, Immunotherapy Response Assessment for Neuro-oncology (iRANO)[1]) for determining disease progression is not optimal for PVSRIPO-based therapy; see **Table 3** for modified response criteria.
- The time to objective radiographic anti-tumor response ranged from approximately 5 to 29 months post-infusion in the Recurrent Glioblastoma (rGBM) PVSRIPO Phase 1 study (Pro00031169; median time to response 15 months).
- For patients to have the best opportunity for an immune-mediated anti-tumor response, experience suggests that patients should be managed as noted below and as outlined in the protocol.

**Treatment emergent adverse events should be managed at the discretion of the principal investigator, with patient safety being the primary consideration. Based on prior experience, the best recommended management of treatment-induced peritumoral edema or of a pseudopressive, polycystic, expansive-type of tumor appearance (ie, immunoprogession) within 6 months of any PVSRIPO infusion is as follows:**

- **Radiographic findings but patient asymptomatic/stable:**
  - Observe and continue to follow per protocol
- **Radiographic findings with new onset/worsening clinical symptoms:**
  - Preferred: Low dose bevacizumab (7.5mg/kg every (q) 3 weeks; few cycles as possible to achieve symptom control)
  - Initiation of low dose steroids (dexamethasone  $\leq$  4mg/day) if rapid response is clinically indicated
  - Other supportive care treatments, as required (eg, antiepileptics)

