Determination of Sample Size	
Based on an interim summary of the Phase 1 study data of PVSRIPO in rGBM (Pro00031169), an ORR of 11.5% was demonstrated (7/61 patients). With 30 subjects treated in this study, there is >75% power to demonstrate a 20% or greater improvement in ORR with the addition of pembrolizumab (ORR > 31%, two-sided P<0.05).
 
The planned evaluable sample size of 30 patients will allow initial assessment of the anti-tumor response via the criteria noted in Table 3 and survival over time, to inform future study adaptations and/or the sample size and study design of new trials. The design will also allow for assessment of the efficacy, safety and tolerability of PVSRIPO plus pembrolizumab, relative to accumulated experience with PVSRIPO alone (eg, [5], data on file, Istari) and published or other data available with pembrolizumab alone in patients with rGBM (eg, [3]).

Study and Treatment Duration	
Maximum planned duration of follow-up: Up to 24 months (104 weeks). Participants achieving 24 months of follow-up may be offered participation in a roll-over protocol or other mechanism for longer-term follow-up.
 
Planned treatment duration:
 
 
Single PVSRIPO infusion at baseline (retreatment allowed for qualifying patients (ie, no ongoing AE <math>\geq</math> Grade 2 related to peritumoral edema, tolerated initial PVSRIPO infusion well) with enhancing disease <math>\geq</math> 6 months from initial PVSRIPO infusion (with or without post-infusion resection <math>\geq</math> 4 weeks after retreatment); see Section 3).
 
Pembrolizumab (200 mg IV infusion), q 3 weeks up to Week 104 (maximum of approximately 102 weeks of treatment), or until irAE meeting criteria for discontinuation or confirmed progression via criteria noted in Table 3).
 

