 Individuals of childbearing potential, pregnancy test (urine or serum) within 48 h of catheter placement. Repeat every 6 months or any time pregnancy suspected.

 Thyroid panel (at a minimum: TSH and free T4; may include free and total T3) should occur every 6 weeks while patient is receiving pembrolizumab.

 If undetectable anti-tetanus toxoid immunoglobulin G (ATT IgG) at screen, then Tdap booster vaccine > 1 week prior to biopsy/catheter placement.

 LSQ analysis should include the following (both %, and ABS): CD3 T, CD4 T, CD8 T, CD19 B, CD56 NK cells. LSQ should be collected at visit 1 (pre-boost), visit 2 (post-boost), and before pembrolizumab doses at visits 5 and 6.

 Collection of whole blood for biomarker analyses where indicated. Collected at visit 1 (pre-boost) and visit 2 (post-boost), before pembrolizumab doses at visits 5, 6, 8, and at End of Study visit for progression.

 MRI with and without contrast. Screening MRI conducted within 14 days prior to catheter placement. If neurologic deficit presents at visit 5 and pembrolizumab dose is held to days 15 to 28, MRI should be conducted and precede pembrolizumab administration. After week 11, MRI to occur every 9-12 weeks or more frequently, at the discretion of the treating physician.

 CT occurs before infusion to confirm placement criteria and after catheter is removed, post-infusion, to confirm no bleeding.

 If possible, up to 3 additional core biopsies will be obtained for biomarker testing (if not available from archival tissue obtained within 6 weeks).

 Results from an unscheduled or unplanned biopsy and/or surgical resection should be recorded in the eCRF, and remaining tissue may be requested for analysis.

 PVSIPO retreatment may be allowed for confirmed progression  $\geq$  12 months post-initial PVSIPO infusion with Sponsor/designee approval.

 All visit assessments should be conducted before pembrolizumab administration. Pembrolizumab should be administered every 3 weeks  $\pm$  1 week through week 104, with the first dose at day 14 but up to day 28, if required. If pembrolizumab is permanently discontinued, then safety laboratory evaluations that are not SOC are no longer required 30 days after the date of pembrolizumab discontinuation.

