**Biopsy(ies):**

If there is no confirmation of diagnosis via histology based on a tissue sample obtained within 6 weeks prior to planned infusion, a biopsy will be conducted prior to catheter placement and PVSRIPO infusion to confirm active tumor/high-grade glioma. After the biopsy is performed, the catheter is placed but PVSRIPO may not be infused until the qualifying diagnosis is made.

If the biopsy at catheter placement does not confirm active tumor/high-grade glioma by the site pathologist, the patient will not receive PVSRIPO and will be withdrawn from the study as a screen failure. The catheter should be removed and followed by a CT scan to confirm no bleeding.

Note: for all patients, including patients with tumor transformed from a lower grade to a higher grade, glioblastoma must be confirmed via prior histology by the site pathologist prior to biopsy/catheter placement.

Stereotactic biopsy(ies) and catheter placement will be performed via the site's standard of care prior to PVSRIPO administration, unless specified below.

- After biopsy for confirmation of diagnosis (if required), if there is sufficient tissue available, up to three additional core biopsies will be obtained to undergo planned future molecular genetic testing as described in **Section 5.7.4**. If no additional biopsies are obtained but archival tissue is available within 6 weeks prior to infusion, that tissue will be requested/utilized for future testing.
  - For patients retreated with PVSRIPO, tissue for tumor typing and clinical pathologic testing per SOC should be obtained prior to the infusion and results reported on the electronic case report form (eCRF) when available
  - Note: results from any analyses conducted on tissue from other biopsies or unplanned surgical resections for the duration of a patient's follow-up should be recorded in eCRF and remaining tissue may be requested for analysis

- The biopsy needle and catheter will be placed by the trained operating surgeon with stereotactic guidance using a MRI-compatible stereotactic head frame or a similar frameless device, and an Food and Drug Administration (FDA) cleared stereotactic guidance system guided by a pre-operative MRI.

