## Planned Treatment:

- Pembrolizumab (200 mg IV) treatment is planned to occur every 3 weeks up to a maximum of Week 104 (24 months).
  - Patients who remain on pembrolizumab will report for infusions every 3 weeks. If pembrolizumab is permanently discontinued, then safety laboratory evaluations that are not SOC are no longer required after 30 days from the date of pembrolizumab discontinuation. See **Sections 5.5** and **5.6** for patients who permanently discontinue or interrupt pembrolizumab treatment before and after study Week 11.
- In general, patients who discontinue pembrolizumab treatment and/or are no longer in the per protocol population (ie, have initiated non-study tumor treatments; see **Section 8**) should be followed per SOC, as possible/feasible.
- If approved by Sponsor or designee, patients with confirmed progression meeting the key safety and infusion related eligibility criteria may be eligible for retreatment with PVSRIPO,  $\geq$  3 weeks after their last pembrolizumab treatment under this protocol.
  - Treatment with pembrolizumab or other treatments after PVSRIPO retreatment will be at the discretion of the investigator and will be recorded in the eCRF.

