#### **8.4.6.1    Objective Response Rate and Disease Control Rate**

Given PVSRIPO’s pattern of response and mechanism of action (direct tumor cell killing followed by adaptive anti-tumor immune response), PVSRIPO can trigger an inflammatory immune response that is observed on imaging, which can make distinguishing between the inflammatory immune response and progressive disease difficult. This is anticipated to occur to a similar or possibly greater extent when followed by pembrolizumab treatment.

In the Phase 1 and Phase 2 rGBM PVSRIPO clinical trials, an initial increase in the extent of FLAIR abnormalities was observed after PVSRIPO, which resolves over time. In addition, an initial increase in size of the enhancing lesion with multiple cystic degeneration was observed (“swiss cheese” or “honeycomb” appearance), as well as an extension of enhancing disease toward previously non-enhancing infiltrative disease, followed by a tumor retraction; see [Figure 4](#). Depending on the size of the tumor, the inflammatory changes could be observed up to 12 months post-PVSRIPO infusion.

This immunopressive appearance can resolve and patients may go on to have an ORR and achieve long-term survival [5]. However, the time to response is delayed, as noted for other immune-therapies [27]; the median time to response in the Phase 1 study based on an ongoing analysis was 15.4 months (range 5.7 to 29.7 months; data on file, Istari). In addition, areas of new enhancement in the vicinity of the target lesion and in previously non-enhancing T2/FLAIR and response tracking, where previously non-enhancing/infiltrative disease enhances and subsequently resolves, has been noted with PVSRIPO in the Phase 1 and Phase 2 rGBM studies within the first 12 months post-infusion and is being independently assessed by central radiographic reviewers (data on file, Istari; see example in [Figure 5](#)). This immunopressive type of radiographic appearance has been described with other immunotherapeutics [1, 30-32].

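### The Protocol gives conflicting rules for PVSRIPO retreatment: 6 or 12 months, and enhancing disease or confirmed progression

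*Protocol*

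**What the plan says.** The Protocol Synopsis (Study and Treatment Duration) permits a second infusion for enhancing disease at or beyond "6 months from initial PVSRIPO infusion (with or without post-infusion resection" and so on, and sends the reader to Section 3. It explains a qualifying patient as one who tolerated the first infusion well and has no ongoing edema-related adverse event of Grade 2 or higher.

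Section 3 says that "retreatment with PVSRIPO is allowed for qualifying patients with enhancing disease" at 12 months or more from the first infusion. After the list of study periods it repeats the 12 months, this time counted from a prior infusion, and allows for more than one further infusion.

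Table 1 footnote 17 allows retreatment for confirmed progression at or beyond "12 months post-initial PVSIPO infusion with Sponsor/designee approval". Section 5.3.4 says that, if the Sponsor or designee approves, "patients with confirmed progression meeting the key safety and infusion related eligibility criteria may be eligible for retreatment with PVSRIPO", at least 3 weeks after the last pembrolizumab dose. It gives no interval from the first infusion.

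The SAP uses 6 months in both places where it mentions retreatment: for progression in 1.1, and for confirmed progression with Sponsor approval in footnote 17 of its Table 1.

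**The concern.** This is the eligibility rule for a second intracerebral infusion, and a site cannot tell from the Protocol when it applies or what triggers it.

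The gap falls in a sensitive period. The Protocol warns of treatment-related enlargement "that can persist for up to 6 or more months after infusion", and Section 8.4.6.1 adds: "Depending on the size of the tumor, the inflammatory changes could be observed up to 12 months post-PVSRIPO infusion". Table 3 accordingly lets an increase in enhancement within 12 months be classed as immunoprogression if it responds to low-dose steroids or bevacizumab. A rule that needs only enhancing disease at 6 months could therefore send a patient for re-infusion when the enhancement is an effect of the first infusion.

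**Working it through.** No figure in the plan bears on this point, so the check sets the texts side by side and adds simple date arithmetic.

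| Place | Earliest time | Trigger | Sponsor approval |
|---|---|---|---|
| Protocol Synopsis | 6 months from first infusion | enhancing disease | not mentioned |
| Protocol 3, treatment bullet | 12 months from first infusion | enhancing disease | not mentioned |
| Protocol 3, line on further infusions | 12 months from a prior infusion | enhancing disease | not mentioned |
| Protocol Table 1, footnote 17 | 12 months from first infusion | confirmed progression | required |
| Protocol 5.3.4 | silent (3 weeks from last pembrolizumab) | confirmed progression | required |
| SAP 1.1 | 6 months from first infusion | progression | not mentioned |
| SAP Table 1, footnote 17 | 6 months from first infusion | confirmed progression | required |

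**Timing.** Planned follow-up is up to 24 months. The retreatment window is 24 − 6 = 18 months under the Synopsis and SAP, and 24 − 12 = 12 months under Section 3 and footnote 17. The difference is 6 months (months 6 to 12), all within Table 3's 12-month immunoprogression window.

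**Trigger.** Table 3 gives an increase up to 3 months to respond to low-dose treatment. It requires the scan that confirms progression to be at least 3 months after the first, unless clinical deterioration prevents it. If an increase is first seen at month t, the earliest confirming scan is at t + 3:

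- t = 3: month 6. Confirmation is possible by the time the 6-month rule opens.
- t = 6: month 9. The Synopsis would allow re-infusion 3 months before that scan.
- t = 9: month 12. This is the latest onset that can be confirmed by the time the 12-month rule opens.
- t = 11: month 14. A 12-month rule based on enhancing disease alone would also open before that scan.

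So the interval alone does not settle the matter. Requiring confirmed progression does, whichever interval is chosen.

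**Precedence.** Protocol Section 8 says the SAP prevails where the two differ. That clause sits in the statistical section, while SAP Section 1 refers the reader to the Protocol for study conduct. The SAP (23 June 2022) also postdates Protocol Version 4 (21 May 2021). Even if the SAP prevailed, the Protocol would still disagree with itself.

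**Starting point.** For a second infusion, counting from the first or from a prior infusion gives the same date. For a third it does not: the count from the first infusion may already be satisfied when the count from the most recent one is not.

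**The case against.** The strongest reply is that the texts can largely be read together. Section 5.3.4 is silent on months, and silence is not a rival rule. It agrees with footnote 17 on trigger and approval. The Synopsis and Section 3 both speak of qualifying patients, which leaves room for the fuller conditions elsewhere. A site that applied the strictest combination would breach nothing. This stands in part, but no text tells a site to combine the conditions, and 6 and 12 months cannot both be the minimum.

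The safety scenario is also a selected case. It needs an increase first seen around month 6 and a site that reads the Synopsis alone. Section 5.2.1 adds a safeguard: "For patients retreated with PVSRIPO, tissue for tumor typing and clinical pathologic testing per SOC should be obtained prior to the infusion". The same section bars infusion until a qualifying diagnosis is made. That wording fits the first infusion best but is not expressly limited to it. These are real mitigations, and they reduce the risk without removing the conflict.

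The 12-month anchor can be challenged too. The SAP's efficacy definitions use unmodified iRANO, whose confirmation requirement covers the first 6 months of immunotherapy, and SAP Section 6 drops the Table 3 analyses. This weakens the case for preferring 12 months. It does not change which criteria sites use, because Protocol 5.7.2 has investigators record response by Table 3.

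A reader might infer three stronger points that the documents do not support:

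- **That each place states its own incompatible rule.** The conflict is on two points, timing and trigger, plus the starting point within Section 3.
- **That retreatment has no eligibility criteria.** Inclusion criterion 8, exclusion criteria 1 and 5 and Section 5.1.1 carry retreatment provisions, although they are not gathered in one list.
- **That the response rate is biased.** SAP 5.7.1.1 does not say how a response first seen after retreatment is scored. But the number retreated is not given, and SAP 5.7.1.2 plans an exact confidence interval with no test. This is missing detail with no shown effect.

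**Conclusion.** The concern holds as a conflict in conduct rules. The minimum interval is 6 or 12 months and the trigger is enhancing disease or confirmed progression, depending on where one reads. At least one stated interval must be wrong. The size is 6 disputed months out of 24, all inside Table 3's immunoprogression window.

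The safety consequence depends on a site following the Synopsis alone, and it is partly mitigated. Nothing in the documents shows that a patient was re-infused in the disputed period. The point should be corrected. It does not undermine the primary analysis.

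**What to change.** State one rule in the Synopsis, Section 3, Table 1 footnote 17 and Section 5.3.4 of the Protocol, and in SAP 1.1 and SAP Table 1 footnote 17. The rule should:

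- require confirmed progression per Table 3 and Sponsor or designee approval;
- set one minimum interval, counted from the most recent infusion;
- keep the Synopsis edema and tolerability conditions and the 3-week gap after pembrolizumab.

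The interval is the sponsor's choice. Twelve months satisfies every current text and matches Table 3's window, but removes re-infusion for true progression in months 6 to 12. Six months matches the Synopsis and SAP and keeps that option. With confirmed progression required, it no longer rests on enhancement alone.

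The cost is a Protocol clarification in four places and matching SAP wording, with no new data. As an optional clarification, SAP 5.7.1.1 could say how a response first seen after retreatment is scored. Infusions are already in Listing 16.2.5.1.2.
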